#### 4.4 Exploratory Endpoints

- The subject incidence with a sustained platelet count of  $\geq 50 \times 10^9/L$  for 6 months or greater without any use of ITP medications (concomitant, rescue, or romiplostim )
- An onset of a sustained platelet response is defined as consecutive platelet counts  $\geq 50 \times 10^9/L$  in the absence of any ITP medications (including romiplostim and other concomitant or rescue medications for ITP). Number and percentage of subjects who have an onset of a sustained platelet response and maintained for at least 24 weeks are summarized.
- The incidence of splenectomy during the treatment period for subjects entering the study pre-splenectomy
- Number and percentage of subjects who did not undergo a splenectomy before study enrollment and had a splenectomy during treatment period are summarized.
- The subject incidence of romiplostim self-administration
- Number and percentage of subjects who initiated self-administration during treatment period are summarized.

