3.1.1 Subjects With an Onset of Sustained Platelet Response

During the treatment period, romiplostim doses will be adjusted as outlined in [Table 1](#). Subjects who dose reduce romiplostim such that they no longer require treatment with romiplostim, no longer require ITP medications (concomitant or rescue), and have an onset of a sustained platelet response (defined as a consecutive platelet counts $\geq 50 \times 10^9/L$) will be monitored for at least 6 months beginning with the first platelet count $\geq 50 \times 10^9/L$. Subjects whose platelet count remains $\geq 50 \times 10^9/L$ in the absence of any medications for ITP for at least 6 months will then be followed every 12 weeks for the duration of the 36-month treatment period.

If during the 36-month treatment period the platelet count subsequently falls below $< 50 \times 10^9/L$, treatment with romiplostim at the initial starting dose may be resumed. Subsequent doses will be adjusted as shown in [Table 1](#). Clinic visits will be resumed per the Schedule of Assessments ([Table 2](#)).

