3.5 Estimated Study Duration

3.5.1 Study Duration for Participants

For an individual subject, the length of participation includes a 4-week screening period, up to a 36-month treatment period, an EOT visit, and an EOS visit. The maximum duration for a subject completing the study will be approximately 3 years and 2 months.

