7.1 Schedule of Assessments

The Schedule of Assessments is found in [Table 2](#) below.

Table 2. Schedule of Assessments

Procedures	Screening	In Clinic Dosing Period ^a	Romiplostim Treatment Period (up to 36-months) ^b			End Of Treatment Visit	End of Study Visit
	- 4 Weeks	Week 1 to Week 8	Weekly	Every 4 Weeks	Every 12 Weeks		
Informed consent	X						
Confirmation of primary ITP diagnosis	X						
ITP/medical history	X						
Physical exam	X				X	X	
Vital signs	X				X	X	
Weight	X				X		
Central lab CBC with differential	X	X ^c		X ^b		X	
Central lab blood (serum) chemistry	X				X	X	
Local lab platelet counts	X	X	X ^{b,d}			X	X
Local lab peripheral blood smear		X ^c		X ^b		X	
Pregnancy test	X				X ^f	X ^f	
Concomitant /rescue medications	X	X	X	X	X	X	X
Adverse event reporting		X	X	X	X	X	
Serious adverse events	X	X	X	X	X	X	X
Antibody sample ^e		Day 1 (before first dose)			W12, W52 and every 24 weeks thereafter	X	
Romiplostim dosing		X	X				

ITP = immune thrombocytopenia; CBC = complete blood counts

- ^a Week 1 to Week 8. All subjects will return to the clinic for weekly dosing of romiplostim, platelet counts by a local laboratory, recording of concomitant/rescue medications, and adverse event reporting.
- ^b Subjects who complete 6 months of sustained platelet response (platelet count $\geq 50 \times 10^9/L$ in the absence of romiplostim or any ITP medications) will have assessments every 12 weeks for the duration of the 36-month treatment period.
- ^c Central CBC with differential and local lab peripheral blood smears are to be performed every 4 weeks, including pre-dose at week 1. Screening laboratory studies may be used in lieu of the pre-treatment day 1 week 1 laboratory tests if performed within 10 days prior to the first dose. Bone marrow biopsy suggested if abnormalities detected.
- ^d For subjects who establish a stable dose of romiplostim and are self-administering, have the injection administered by a caregiver, or meet this criterion but still prefer to come to the clinic for romiplostim administration, platelet counts will be monitored every 4 weeks.
- ^e For subjects who test positive for antibodies, see [Section 7.1.3](#). Antibody sampling during romiplostim treatment is only conducted if subject is receiving study drug.
- ^f Local lab urine or serum pregnancy test for female subjects of child-bearing potential (defined as having first menses)

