10.1 Study Endpoints, Subsets, and Covariates

10.1.1 Study Endpoints

Primary Endpoint:

- The percentage of time with a platelet count of $\geq 50 \times 10^9/L$ starting from week 2 in the first 6 months of the treatment period without rescue medication use within the past 4 weeks

Secondary Endpoints:

- The percentage of time with a platelet count of $\geq 50 \times 10^9/L$ starting from week 2 until the end of the treatment period without rescue medication use within the past 4 weeks
- The percentage of time with an increase in platelet count $\geq 20 \times 10^9/L$ above baseline starting from week 2 until the end of the treatment period without rescue medication use in the past 4 weeks.
- Subject incidence of rescue ITP medications used
- The incidence of anti-romiplostim neutralizing antibodies and cross reactive antibodies to TPO at any time during the study
- The incidence of adverse events, including clinically significant changes in laboratory values

Exploratory Endpoints:

- The subject incidence with a sustained platelet count of $\geq 50 \times 10^9/L$ for 6 months or greater without the use of any ITP medications (concomitant, rescue, or romiplostim)
- The incidence of splenectomy during the treatment period for subjects entering the study pre-splenectomy
- The subject incidence of romiplostim self-administration

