### **10.5 Efficacy Analyses**

The efficacy analysis will be based on the Efficacy Analysis Set, which includes all subjects who receive at least one dose of romiplostim.

Summary statistics of platelet counts and responses will be provided weekly at Week 1 to 8 and then every 4 weeks for all subjects in the efficacy analysis set and by age groups (<6, 6-<12, 12-<18 years). Platelet response is defined as platelet count

---

$\geq 50 \times 10^9/L$ . Platelet counts within 4 weeks after rescue medication use will not be deemed as platelet responses.

The percentage of time with platelet response starting from Week 2 in the first 6 months of the treatment period will be estimated for all treated subjects and by age groups (<6, 6-<12, 12-<18).

The percentage of time with platelet response from Week 2 till the end of the treatment period will be estimated for all treated subjects and by age groups (<6, 6-<12, 12-<18).

The percentage of time with an increase in platelet counts  $\geq 20 \times 10^9/L$  above baseline starting without rescue medication use during past 4 weeks from Week 2 until the end of the treatment period will be estimated for all treated subjects and by age groups (<6, 6 <12, 12-<18).

The proportion of subjects who used rescue medication for ITP during the study will be summarized by preferred terms. Rescue medication is defined as any medication or transfusion, other than romiplostim and excluded medications, that is administered after enrollment to the subject during screening or throughout the treatment period with the intent of raising platelet counts or prevent bleeding and includes concomitant medications for ITP where the dose and/or schedule is increased.

The proportion of subjects who achieved sustained platelet response for 24 weeks or longer will be summarized. A sustained platelet response is defined as a platelet count  $\geq 50 \times 10^9/L$  without the use of any ITP medications.

The proportion of subjects who had a splenectomy during the study will be summarized for the subjects who entered this study without splenectomy.

Number and percentage of subjects who started self-administration of romiplostim during the study will be summarized.

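### The SAP counts a sustained off-treatment response from 24 weeks, about two weeks short of the 6 months that the protocol and the SAP's own endpoint bullet require, and does not declare the difference

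*SAP*

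**What the plan says.** Protocol 10.1.1 defines the exploratory endpoint as the subject incidence of a platelet count sustained at or above 50 x 10^9/L "for 6 months or greater without the use of any ITP medications". The endpoint bullet in SAP 4.4 says the same: "for 6 months or greater without any use of ITP medications".

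The protocol's follow-up rules use the same duration. Under 3.1.1, children with an onset of sustained response "will be monitored for at least 6 months beginning with the first platelet count" at the threshold, and those who hold it "in the absence of any medications for ITP for at least 6 months will then be followed every 12 weeks". Footnote b to Table 2 (section 7.1) applies the 12-weekly schedule to "Subjects who complete 6 months of sustained platelet response".

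The SAP's counting rules differ. The text under the 4.4 bullet takes subjects whose response is "maintained for at least 24 weeks are summarized". SAP 10.5 states: "The proportion of subjects who achieved sustained platelet response for 24 weeks or longer will be summarized".

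SAP 6 defines study day, study week 1 and the treatment period, but not a month. SAP 11 states that nothing departs from the protocol's analyses.

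**The concern.** The declared endpoint and the rule that will be programmed are not the same length, and the SAP does not say that one stands for the other. For a given onset date and set of counts, a shorter required duration can only add responders, so any error runs in one direction. A child who holds the threshold through week 24 and falls below it in week 25 or 26, or whose follow-up ends then, is counted by the SAP and not by the endpoint.

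At stake is how the result is described. Off-treatment response in children is likely to be quoted on its own, and under the SAP's bullet it would be quoted as lasting 6 months or more. The numerator may be small, so one or two children matter more to this figure than to a summary over all 200.

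**Working it through.** **The plan's own figure.** The only precision figure is for the primary endpoint: a half width of 4% to 5% with 200 subjects and an SD of 30% to 36%. It reproduces: 1.96 × 30 / √200 = 4.16% and 1.96 × 36 / √200 = 4.99%. It has no bearing on the sustained-response endpoint, for which the plan gives no expected rate or precision.

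**Could the two durations be the same?** This depends on the length of a month.

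- Calendar month: 6 × 365.25/12 = 182.6 days = 26.1 weeks. The SAP rule is 24 × 7 = 168 days = 5.52 months. The gap is 14.6 days, or 2.09 weeks, which is 8.0% of 182.6 days.
- Four-week month: 6 × 4 = 24 weeks, and the gap is zero.

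The documents can be tested against both. Protocol 3.5.1 gives "up to a 36-month treatment period", and protocol 3.1 gives the same period as three years. Thirty-six four-week months would be 144 weeks, or 2.76 years; thirty-six calendar months are 156.5 weeks, or 3 years. The regional supplement's schema likewise places the Year 2 biopsy cohort at 24 months. The calendar reading fits better.

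**Is it a version difference?** The SAP cites the protocol of 15 January 2014. The change descriptions for Amendments 1 and 2 list no edit to this endpoint, so the mismatch does not come from an amendment.

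**Relapse in the gap.** The documents give neither the number reaching week 24 nor a relapse rate. Assumptions: n = 10 to 50 of 200 children reach week 24 off all ITP medication, and a constant risk with a fraction r losing response per 6 months, r = 10% to 50%. Then P(loss in gap) = 1 − (1 − r)^(2.09/26.09).

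| r | P(loss in gap) | n = 10 | n = 30 | n = 50 |
|---|---|---|---|---|
| 10% | 0.84% | 0.08 | 0.25 | 0.42 |
| 30% | 2.82% | 0.28 | 0.84 | 1.41 |
| 50% | 5.40% | 0.54 | 1.62 | 2.70 |

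**Follow-up ending in the gap.** If onsets are spread evenly over the 36 months, the share whose follow-up ends between week 24 and month 6 is 2.09/156.5 = 1.3%, or 0.13 of 10 children and 0.67 of 50. Restricting to onsets early enough to reach week 24 gives 2.09/(156.5 − 24) = 1.6%, or 0.16 to 0.79; the picture is the same.

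**Together.** 0.08 + 0.13 = 0.2 children at the low end and 2.70 + 0.67 = 3.4 at the high end. Each child is 0.5 percentage points of 200.

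**The case against.** The best defence is that 24 weeks is a nominal half-year. Visits, antibody sampling and platelet summaries run in 4-, 12- and 24-week units, neither document defines a month, and protocol 3.5.1 reaches its total of roughly 3 years and 2 months by treating the 4-week screening period and the final 4 weeks loosely as two months. A result reported openly as 24 weeks would be correct for its label. The endpoint is also exploratory and descriptive, with no test and no success criterion, so no decision in the plan turns on it.

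Most of this stands as a limit on importance. The convention is plausible, but it is nowhere stated, and it conflicts with 36 months being 3 years. The label does not rescue it either, because the bullet above the rule calls the endpoint 6 months and SAP 11 reports no change.

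A further fair objection concerns the remedy. Requiring at least 183 days and a qualifying count on or after that day would create a new mismatch. Six calendar months run from 181 to 184 days, a week-26 count falls on day 182, and after 6 months visits move to every 12 weeks, so true 6-month responders could be missed. The remedy has to avoid this.

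**Conclusion.** The inconsistency is real, appears twice in the SAP and is not declared. Its effect is small: about 0.1 to 2.7 children relapsing in the gap plus about 0.1 to 0.7 whose follow-up ends in it. This rests on calendar months and on assumed values for the number reaching week 24, the relapse risk and the spread of onsets. It is a minor point, worth correcting because correction is nearly free.

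Three stronger readings are tempting and are not supported.

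- A reader might infer that every child who stops treatment less than 6 months before month 36 is added. A child off treatment for 4, 12 or 20 weeks at month 36 fails the 24-week rule as well. Only a window of about 15 days is affected.
- A reader might infer that counts come every 4 weeks, so that week 28 is the first count able to confirm 6 months. Footnote d to Table 2 gives the 4-weekly interval to children on a stable romiplostim dose. Under protocol 7.6, children who have stopped all ITP medication stay on the schedule of assessments, which lists weekly counts, so counts at weeks 25 to 27 are expected.
- A reader might infer that the table will broadly disagree with the list of children moved to 12-weekly visits. Every child who completes 6 months also meets 24 weeks, so the two differ only by the few children in the gap.

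**What to change.** In SAP 4.4 and 10.5, replace 24 weeks with 6 months (26 weeks, allowing the protocol's ±1 day visit window). Measure the period from the first platelet count of at least 50 x 10^9/L off all ITP medication to the last consecutive qualifying count. Twenty-six weeks less one day is 181 days, the shortest that six calendar months can be, so a child with a qualifying week-26 visit is not lost. Under this definition a child whose follow-up ends before the threshold is not counted as a sustained responder; the SAP should say so.

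If the sponsor prefers 24 weeks, label the result as 24 weeks wherever it is reported and list it in SAP 11 as a change from the protocol endpoint.

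Either option is a wording change in the SAP. It needs no new data and leaves visits and treatment as they are. With the first option, the reported incidence may be slightly lower.

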#### 5. Hypotheses and/or Estimations

The statistical analysis in this open-label study will be descriptive in nature and no hypothesis testing is intended. The percentage of time with a platelet response in the first 6 months of the study will be estimated. Categorical data will be presented in the form of number and percentage. Continuous data will be provided with the descriptive statistics (n, mean, standard deviation, median, Q1 [25th percentile], Q3 [75th percentile], minimum, and maximum).

#### 6. Definitions

| Term                                      | Definition/Explanation   |
|---|--|
| End of study for individual subject (EOS) | Defined as the last day that protocol-specified procedures are conducted for an individual subject   |
| End of treatment (EOT)                    | Defined as the last assessment for the protocol-specified treatment phase of the study for an individual subject   |
| End of study (primary completion)         | Defined as the time when the last subject is assessed or receives an intervention for the purposes of final collection of data for the primary outcome. This will occur once the last subject participating has completed the EOS visit. |
| Interactive Voice Response System (IVRS)  | Telecommunication technology that is linked to a central computer in real time as an interface to collect and process information.   |

| Term                                      | Definition/Explanation   |
|---|--|
| Study Day 1                               | Defined as the first day that romiplostim is administered to the subject   |
| Study Week 1                              | Defined as the week that the first dose of romiplostim is administered to the subject                                    |
| Study day                                 | Defined as (calendar date – first dose date) +1  |
| Study treatment period                    | Defined as the period from the date of first dose of romiplostim till the date of last dose of romiplostim plus one week |
| Treatment duration for individual subject | Defined as the (last dose date – first dose date)+7 days   |
| Baseline Platelet Count                   | The average of available platelet counts obtained at screening and pre-treatment prior to dosing.                        |
| Study baseline                            | Other than for platelet count, the baseline is defined as data immediately prior to first dose administration            |
| Platelet response                         | Defined as platelet count of $\geq 50 \times 10^9/L$ without rescue medication use for ITP in the past 4 weeks           |

Page 2 of 2

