6.4 Concomitant Therapy

Throughout the study, investigators may prescribe any concomitant medications or treatments deemed necessary to provide adequate supportive care, except for those listed in [Section 6.6](#).

All prescription and non-prescription concomitant medications, used to treat conditions other than ITP, administered at the time of enrollment, ongoing after enrollment, as well as changes in such concomitant medications and any new concomitant medications taken while the subject is on study, will be recorded on the appropriate eCRF through the EOT or the EOS visit, whichever is later.

Concomitant and Rescue Therapy for ITP

Concomitant medications are allowed for subjects enrolled into the study in any situation deemed medically necessary to increase platelet counts. Medications to increase platelet counts starting before enrollment and continuing unchanged (dose and schedule) while on treatment with romiplostim will be defined as concomitant medications for ITP. Rescue medication is defined as any medication or transfusion, other than romiplostim and excluded medications, that is administered after enrollment to the subject with the intent of raising platelet counts or to prevent bleeding and includes concomitant medications for ITP in which the dose and/or schedule is increased. For the purposes of this study, the permitted rescue medications include the following:

- corticosteroids
- platelet transfusions
- IVIG
- azathioprine
- anti-D immunoglobulin
- danazol

Antifibrinolytics can be used at any time during the study and will not be considered rescue medication(s).

Inhaled and/or topical corticosteroids intended to treat non ITP conditions (eg, inhaled steroids for asthma) will not be considered concomitant medications for ITP or rescue

Product: Romiplostim
Protocol Number: 20101221
Date: 15 August 2014

Page 30 of 69

medications and continuing on such medication(s) will not affect the definition of platelet response.

Rescue medication is allowed throughout the duration of the study when platelet counts are $< 20 \times 10^9/L$ and/or when a subject has bleeding or wet purpura. Rescue medication is also allowed in any situation deemed medically necessary by the treating physician to increase platelet counts to treat or prevent bleeding.

Reduction or discontinuation of concomitant or rescue medications for ITP is recommended based on investigator judgment when platelet counts are $\geq 50 \times 10^9/L$.

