7.5 Screening

The screening period begins on the date that the subject (and/or the subject's legally authorized representative) signs the IRB/IEC-approved informed consent form and continues until the date of enrollment. Procedures that are part of routine care are not considered study-specific procedures. All subjects will be screened for eligibility before enrollment.

The following screening procedures must be completed within 4 weeks before the day of first dose of romiplostim:

- informed consent (and assent if required by IRB/IEC)
- confirmation of ITP diagnosis
- ITP and medical history
- physical exam as per standard of care including weight and vital signs. Physical examination findings should be recorded on the medical history or adverse event eCRF
- concomitant medications
- central lab CBC with differential and blood chemistry
- confirmation of one local lab platelet count $\leq 30 \times 10^9/L$ and/or documentation of bleeding that was uncontrolled with conventional therapies for ITP
- local lab urine or serum pregnancy test for female subjects of child-bearing potential (defined as having first menses)
- serious adverse events that occurred after the signing of informed consent

If subjects do not successfully complete screening within 4 weeks after initial informed consent, their screen failure will be registered in the IVRS. Subjects who fail screening will be allowed to re-screen. Subjects who rescreen must repeat relevant screening procedures within the new 4-week screening window. If the subject's screening platelet count is $> 30 \times 10^9/L$ without evidence of uncontrolled bleeding with conventional

Product: Romiplostim
Protocol Number: 20101221
Date: 15 August 2014

Page 38 of 69

therapies upon initial assessment the site may reassess the platelet count during the 4-week screening period without registration of screen-failure or re-consenting the subject.

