## **4. Study Endpoints and Covariates**

### **4.1 Study Endpoints**

#### **4.2 Primary Endpoint**

The primary endpoint is the percentage of time with a platelet response, defined as a platelet count of  $\geq 50 \times 10^9/L$  without rescue medication use for ITP in the past 4 weeks, starting from Week 2 in the first 6 months of the treatment period.

A rescue-evaluable weekly platelet count is defined as a weekly platelet count without rescue medication use for ITP in the past 4 weeks.

In the first 6 months of treatment period, a monthly platelet response is defined as a the median of rescue-evaluable platelet counts of  $\geq 50 \times 10^9/L$ .

For each subject, the percentage of time with platelet response during the first 6 months is calculated as the number of monthly platelet response divided by the total number of months. If the monthly platelet response is missing, it will be imputed based on the neighboring monthly platelet response status and rescue medication use in the month. If a monthly platelet response is still missing after imputation, it is considered as no response in this month. Subjects who discontinued the treatment early due to lack of

response (non-responder to romiplostim) before completing 6 months of treatment, the month(s) following their discontinuation of treatment till the 6th month will be imputed as having no monthly platelet response.

The primary endpoint is summarized by descriptive statistics (n, mean, standard deviation, median, Q1 [25th percentile], Q3 [75th percentile], minimum, and maximum) of this percentage of time with platelet response averaging across subjects.

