#### 4.3 Secondary Endpoints

- The percentage of time with platelet response starting from Week 2 until the end of the treatment (EOT) period.
- For each subject, the percentage of time with a platelet response from Week 2 till EOT is calculated as the number of weeks with a platelet response divided by the total number of weeks. Weekly platelet counts are imputed by last observation carry forward using rescue-evaluable weekly platelet counts during the treatment period.
- Descriptive statistics (n, mean, standard deviation, median, Q1 [25th percentile], Q3 [75th percentile], minimum, and maximum) are provided for the average percentage of time across subjects.
- The percentage of time with an increase in platelet count  $\geq 20 \times 10^9/L$  above baseline starting from Week 2 until the end of the treatment period without rescue medication use for ITP in the past 4 weeks.
- For each subject, the percentage of time with an increase in platelet count  $\geq 20 \times 10^9/L$  above baseline from Week 2 till EOT is calculated as the number of weeks with an increase in platelet count  $\geq 20 \times 10^9/L$  above baseline divided by the total number of weeks. Weekly platelet counts are imputed by last observation carry forward using rescue-evaluable weekly platelet counts during the treatment period.
- Descriptive statistics (n, mean, standard deviation, median, Q1 [25th percentile], Q3 [75th percentile], minimum, and maximum) are provided for the average percentage of time across subjects.
- Subject incidence of rescue ITP medications used.
- Total number and percentage of subjects who reported any usage of rescue medications for ITP are calculated with a sub-categorization by preferred terms.
- The incidence of anti-romiplostim neutralizing antibodies and cross reactive antibodies to TPO at any time during the study.
- Number and percentage of subjects who developed anti-romiplostim neutralizing antibodies and/or cross reactive antibodies to TPO by study visits are calculated.
- The incidence of adverse events, including clinically significant changes in laboratory values.

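### The baseline for the +20 × 10⁹/L secondary endpoint has no filter for counts transiently raised by pre-dose ITP treatment, so an affected child's threshold is set too high

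*SAP*

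**What the plan says.** SAP section 6 sets the baseline platelet count as "The average of available platelet counts obtained at screening and pre-treatment prior to dosing". The protocol gives no definition of its own.

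The baseline feeds one efficacy endpoint. In SAP section 4.3 a child's result is the "number of weeks with an increase in platelet count" of at least 20 × 10⁹/L, divided by all weeks, with the rise measured "above baseline starting from Week 2 until the end of the treatment period without rescue medication use for ITP" in the past 4 weeks. No rule resets the baseline later.

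The SAP does filter counts taken after dosing. Section 4.2 states: "A rescue-evaluable weekly platelet count is defined as a weekly platelet count without rescue medication use for ITP in the past 4 weeks". Section 4.3 carries the last observation forward "using rescue-evaluable weekly platelet counts during the treatment period". Section 10.5 does not accept a count within 4 weeks after rescue medication as a response.

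On what may happen before dosing:
- Protocol 3.1 lets children enter on platelet-raising medication and stay on it.
- Protocol 4.2 sets washouts for eltrombopag, rituximab, 6-mercaptopurine and alkylating agents. It sets none for steroids, IVIG, anti-D or transfusion.
- Protocol 4.1 and 7.5 require one count of 30 × 10⁹/L or less, or uncontrolled bleeding. If the first count is above 30 without such bleeding, "the site may reassess the platelet count during the 4-week screening period", so several counts can enter the mean.

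**The concern.** The endpoint is a difference, and only one side of it is protected. A count lifted for a short time by treatment other than romiplostim cannot be a response after dosing, yet the same kind of count before dosing is averaged into the reference value. That raises the bar the child must clear, and because the baseline is fixed, the bar stays raised for a treatment period of up to 36 months. The child's percentage of time with a rise of at least 20 is then understated. The baseline platelet summary in SAP section 10.4 also overstates that child's untreated count.

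**Working it through.** The plan gives no figure on this point. The nearest is the precision planned for the primary endpoint (Protocol 10.2, SAP 3.2), useful only for scale. With n = 200, the half width is 1.96 × SD / √200:
- SD 30: 1.96 × 30 / 14.14 = 4.16 points
- SD 36: 1.96 × 36 / 14.14 = 4.99 points

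This reproduces the stated 4% to 5%.

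**One child.** All counts below are assumed, in units of 10⁹/L. Threshold = baseline mean + 20.
- Counts 12 (untreated) and 110 (shortly after IVIG), current definition: (12 + 110) / 2 = 61, threshold 61 + 20 = 81.
- Treated count left out: 12 + 20 = 32.
- Excess: 81 − 32 = 49. Weeks with counts from 32 to below 81 change class; weeks below 32 or at 81 and above do not.

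**Range.** With one untreated count s and one raised count x, the excess is (s + x)/2 − s = (x − s)/2.

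| Assumed counts | Threshold now | Threshold with raised count excluded | Excess |
|---|---|---|---|
| s = 30, x = 50 | 60 | 50 | 10 |
| s = 5, x = 50 | 47.5 | 25 | 22.5 |
| s = 10, x = 100 | 75 | 30 | 45 |
| s = 30, x = 150 | 110 | 50 | 60 |
| s = 5, x = 150 | 97.5 | 25 | 72.5 |

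Over s from 5 to 30 and x from 50 to 150, the excess is 10 to 72.5. A second untreated count dilutes it without removing it: two counts of 10 or 20 with one raised count of 80 to 150 give an excess of 20 to 46.7.

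**Relation to the ≥ 50 criterion.** The threshold passes 50 when (s + x)/2 > 30, that is when x > 60 − s (x > 50 for s = 10; x > 40 for s = 20). A week can then be a platelet response and still fail the +20 criterion.

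**Cohort mean.** Shift = share of children affected × loss in percentage of time. The documents give neither term. Assuming shares of 2% to 20% and losses of 10 to 50 points:
- lowest: 0.02 × 10 = 0.2 points
- middle: 0.05 × 25 = 1.25 points
- highest: 0.20 × 50 = 10 points

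**The case against.** The best reply is that the gap may seldom matter. No passage says how many children receive a transfusion, IVIG, anti-D or new steroids shortly before the first dose. Dosing aims at counts of 50 to 200, so a child in the example who settles at 81 or above loses nothing. The endpoint is one secondary in a single-arm descriptive study, and the bias cannot exaggerate benefit. All of this stands and limits the weight of the point. It does not make the estimate right for an affected child.

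Several stronger readings are tempting and not supported:
- **That such treatment is likely.** A reader might infer this from the marrow biopsies in the EU, Switzerland and Turkey supplement. No passage links biopsy to platelet-raising treatment, the supplement covers at least 60 of about 200 children, and it accepts a biopsy from the previous year.
- **That the SAP expects rescue before dosing.** SAP 10.5 describes rescue as "administered after enrollment to the subject during screening or throughout the treatment period". But Protocol 7.5 ends screening at enrollment, and Protocol 5 counts a child as enrolled only after the first dose. The SAP wording contradicts these passages and is weak evidence of anything.
- **That the retest in Protocol 7.5 shows treatment-raised counts.** It shows only that more than one count can be available.
- **That +20 was meant as the milder criterion, so a threshold above 50 proves an error.** The documents do not say so. An untreated child who enters with uncontrolled bleeding at a count of 40 has a threshold of 60.
- **That any baseline on steroids is wrong.** A child on unchanged background therapy, which Protocol 6.4 classes as concomitant, has a fair on-background reference.

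One might also argue that the existing 4-week rule covers the baseline. It does not: it applies to weekly counts, the baseline takes in whatever counts are available, and Protocol 6.4 defines rescue as follows: "Rescue medication is defined as any medication or transfusion, other than romiplostim and excluded medications, that is administered after enrollment". Read with Protocol 5, that leaves pre-dose treatment outside the rule.

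**Conclusion.** The point holds in a narrow form. As written, the baseline definition admits counts transiently raised by a transfusion or by newly started or increased ITP medication, the documents allow such treatment before dosing, and nothing elsewhere corrects for it. For an affected child the +20 threshold is too high from Week 2 to end of treatment, by 10 to 72.5 × 10⁹/L over the assumed pairs of counts.

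Only the secondary +20 endpoint and the baseline platelet summary are affected. The primary endpoint uses the absolute threshold of 50 and does not involve baseline. The bias is downward. Its size in the cohort is not identified: the range of 0.2 to 10 points rests wholly on assumed shares and losses. Most of that range lies below the 4 to 5 point half width planned for the primary endpoint, and only the heavier assumptions reach or exceed it.

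**What to change.** Amend the baseline definition in SAP section 6:
- Leave out of the mean any count taken within 4 weeks after a transfusion or after an ITP medication was newly started or increased.
- Keep counts taken on unchanged background therapy.
- Tie the rule to these treatments rather than to the term rescue. Protocol 5, 6.4 and 7.5 and SAP 10.5 conflict on whether treatment before the first dose is rescue, and must be reconciled.
- If no count is left, use the mean of all available counts from before that treatment; failing that, keep the current definition and flag the child. Do not pick the single last count before treatment: it may be the low value that prompted it, and in an uncontrolled study regression to the mean would then favour response.
- Report the +20 endpoint under both the current and the revised definition, with the number of children whose baseline differs.

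The cost is SAP wording and one extra table. Protocol 7.4 records ITP medication from screening and Protocol 7.3 collects prior therapies. A 4-week look-back from an early screening count reaches before screening, however, so it should be checked that start dates and dose changes are captured. Fewer counts will enter some baselines, and the lower baselines may slightly raise the +20 estimate through regression to the mean. Showing both definitions makes the net difference visible.
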